Study Design	
Part 1
 
The study will enrol 48 participants to Part 1. Recruitment will select potential participants who are willing to undergo serial blood draws and mucosal secretion sampling. Additional participants may be enrolled to replace any early withdrawals.
 
Vaccine & Immunisation Schedule for Part 1 & Part 2
 
Table 1
 
  
 Group	N	Month 0	Month 3	Month 6	
   
 A	6	Oral placebo	CN54gp140 +Oral placebo +I.M placebo	CN54gp140 +Oral placebo +I.M placebo	
 
 B	6	Ad4-EnvCN54	CN54gp140 +Oral placebo +I.M placebo	CN54gp140 +Oral placebo +I.M placebo	
 
 C	6	Ad4-EnvCN54	CN54gp140 + Ad4-EnvCN54 + I.M placebo	CN54gp140 +Oral placebo + I.M placebo	
 
 D	6	Ad4-EnvCN54	CN54gp140 + Ad4-EnvCN54 +I.M placebo	CN54gp140 + Ad4-EnvCN54 +I.M placebo	
 
 E	6	Oral placebo	CN54gp140 +MVA-CN54 +Oral placebo	CN54gp140 +MVA-CN54 +Oral placebo	
 
 F	6	Ad4-EnvCN54	CN54gp140 +MVA-CN54 +Oral placebo	CN54gp140 +MVA-CN54 +Oral placebo	
 
 G	6	Ad4-EnvCN54	CN54gp140 +MVA-CN54	CN54gp140 +MVA-CN54	
  
	Group	N	Month 0	Month 3	Month 6	A	6	Oral placebo	CN54gp140 +Oral placebo +I.M placebo	CN54gp140 +Oral placebo +I.M placebo	B	6	Ad4-EnvCN54	CN54gp140 +Oral placebo +I.M placebo	CN54gp140 +Oral placebo +I.M placebo	C	6	Ad4-EnvCN54	CN54gp140 + Ad4-EnvCN54 + I.M placebo	CN54gp140 +Oral placebo + I.M placebo	D	6	Ad4-EnvCN54	CN54gp140 + Ad4-EnvCN54 +I.M placebo	CN54gp140 + Ad4-EnvCN54 +I.M placebo	E	6	Oral placebo	CN54gp140 +MVA-CN54 +Oral placebo	CN54gp140 +MVA-CN54 +Oral placebo	F	6	Ad4-EnvCN54	CN54gp140 +MVA-CN54 +Oral placebo	CN54gp140 +MVA-CN54 +Oral placebo	G	6	Ad4-EnvCN54	CN54gp140 +MVA-CN54	CN54gp140 +MVA-CN54

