## 7.6 CLINICAL STUDY DESIGN

To identify an effective Ad4 based oral vaccine that promotes systemic and mucosal responses to the HIV-1 envelope glycoprotein, our group will adopt a two part adaptive clinical trial. The study will assist in rapidly screening the impact of different routes, combination regimes and boosting options to Ad4-EnvCN54, MVA-CN54 and CN54gp140 / MPLA, to augment systemic and mucosal antibody responses following initial priming with Ad4.

The study will enrol 48 participants to Part 1 and 12 participants in Part 2. Recruitment will select potential participants who are willing to undergo serial blood draws. Additional participants may be enrolled to replace any early withdrawals.

**In Part 1**, n=6 participants per group will be randomised to groups A-H (Table 1). This design varies the number of Ad4 administrations, from 1 to 3, combined with either CN54gp140 protein boosts (A-D) or co-administration of gp140 with MVA (E-H). Groups A (gp140 alone) and E (MVA-CN54/CN54gp140 alone) will serve as control groups to assess the added benefit of the Ad4 vector. Each vaccine group (A-H) will be assessed for number of mucosal responders (mucosal antibody (rectal/genital/nasal) as measured by ELISA), and titre (mucosal and systemic) of antigen specific binding antibody. Based on data from the MUCOVAC2 study, in which participants received 3 intramuscular doses of CN54gp140 with GLA-AF adjuvant, we anticipate that there will be no mucosal responders in group A (although there will be detectable systemic responses). Enrolment through to completion of the primary immunological assessment for each group will be 7 months.

**In Part 2**, the best regimes from A-D (Ad4-EnvCN54/CN54gp140) and E-H (Ad4-EnvCN54/MVA-CN54/CN54gp140) will be expanded to n=12 (additional n=6) in Part 2. Immune responses at the Primary Immunogenicity Endpoint (Week 26) will be analysed. Selection will be based on total number of responders. In the event that more than one group has the same number of responders, mucosal antibody titre will be used to rank groups to determine which to take forward to Part 2. Should mucosal titers be indistinguishable between groups, then serum antibody levels will be taken into consideration in the selection of groups to progress to Part 2.

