## 10 REGISTRATION & DISTRIBUTION INTO TREATMENT GROUPS

### 10.1 RANDOMISATION PRACTICALITIES

#### 10.1.1 PART 1

The enrolment visit will take place within 90 days after the screening visit and will be the same day as the first vaccination. Assessments and procedures will be undertaken according to the schedules in Table 2, and data entered on the CRF.

The study will use sentinel dosing as a safety precaution. The first 6 participants successfully enrolled into the trial will be sequentially pre-allocated to treatment groups B, C, D, F, G and H. The first participant will be enrolled to group B. The safety data for this participant will be reviewed at day 7 before enrolling the next participant to group C. This process will be repeated for the other groups. This will ensure an escalation of the number of Ad4-EnvCN54 administrations combined with either CN54gp140 protein boosts (B-D) or co-administered CN54gp140 and MVA-CN54 (F-H).

After the accumulated safety data (up to day 7) for the 6th participant has been reviewed, on their first day of dosing the remaining participants will be block randomised into groups as follows:

- Block 1 (n=10): A, A, B, C, D, E, E, F, G, H
- Blocks 2-6 (n=8/block): A, B, C, D, E, F, G, H

#### 10.1.2 PART 2

Six additional healthy participants per group will be recruited and randomised to the best two regimes from A-D (Ad4-EnvCN54/CN54gp140) and E-H (Ad4-EnvCN54/MVA-CN54/CN54gp140). The visits schedule for participants in Part 2 will be the same as that for participants in Part 1. Assessments and procedures will be undertaken according to the schedules in Table 2, and data entered on the CRF.

#### 10.1.3 PASS CRITERION FOR PART 2

The group selection for Part 2 is based on results generated from the primary immunogenicity endpoint (Week 26, Visit 9). In the event that more than one group has the same number of responders, mucosal antibody titre will be used to rank groups to determine which to take forward to Part 2. Should mucosal titers be indistinguishable between groups, then serum antibody levels will be taken into consideration in the selection of groups to progress to Part 2. The criterion for a positive mucosal response, and methods for ranking groups on the basis of mucosal and serum antibody titers, will be specified in the LAP. If any groups are associated with unacceptable product related adverse events, they will be discontinued from further study.

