## 14 STATISTICAL CONSIDERATIONS

### 14.1 METHOD OF RANDOMISATION

The first 6 participants successfully enrolled into the trial will be sequentially pre-allocated to treatment groups B, C, D, F, G and H.

Participants thereafter will be block-randomised centrally using a computer-generated algorithm with a back-up manual procedure. Randomisation will be stratified on the basis of gender.

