
5 Randomisation

5.1 Part 1

The study will use sentinel dosing as a safety precaution. The first 6 participants successfully enrolled into the trial will be sequentially pre-allocated to treatment groups B, C, D, F, G and H. The first participant will be enrolled to group B. The safety data for this participant will be reviewed at day 7 before enrolling the next participant to group C. This process will be repeated for the other groups. This will ensure an escalation of the number of Ad4-EnvCN54 administrations combined with either CN54gp140 protein boosts (B-D) or co-administered CN54gp140 and MVA-CN54 (F-H).

After the accumulated safety data (up to day 7) for the 6th participant has been reviewed, on their first day of dosing the remaining participants will be block randomised into groups as follows:

- Block 1 (n=10): A, A, B, C, D, E, E, F, G, H
- Blocks 2-5 (n=8/block): A, B, C, D, E, F, G, H

5.2 Part 2

Participants will be randomised to the groups chosen for expansion. Participants will be blind to the vaccine regime group to which they have been assigned. The laboratory undertaking immunological analysis will also be blinded to group and dosing regimen to prevent bias in analysis.

Six additional healthy participants per group will be recruited and randomised to the best two regimes from A-D (Ad4-EnvCN54/CN54gp140) and E-H (Ad4-EnvCN54/MVACN54/CN54gp140).

The visits schedule for participants in Part 2 will be the same as that for participants in Part 1.

6 Blinding

This is a single-blind, randomised trial with placebo controls. Participants will be block-randomised centrally, using the randomisation schedule produced by the statisticians at the Surrey CTU, to the study groups shown in Table 1, using a computer-generated algorithm with a back-up manual procedure. Randomisation will be stratified on the basis of gender.

All participants in Part 1 and Part 2 will be blinded to the vaccine regime group to which they have been assigned. The laboratory teams undertaking immunological analysis will also be blinded to group and dosing regimen to prevent bias in analysis. The clinical team will remain unblinded to the vaccine regime of trial participants throughout.

7 Replacing Withdrawals

As the number of participants per group is small and hence each participant is essential to the study, those who withdraw from the study will be replaced before completion of the week 26 visit.

8 Study hypothesis

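### Protocol 10.1.1 lists randomisation blocks for 56 participants in Part 1 (7 per group), against the planned 48 (6 per group) that the SAP's block list delivers

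*Protocol*

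**What the plan says.** The enrolment target is consistent across the protocol. Section 7.6 says "The study will enrol 48 participants to Part 1 and 12 participants in Part 2", and for Part 1 that "n=6 participants per group will be randomised to groups A-H". The Summary of Trial, section 9.3 and Table 1 (sections 3 and 11.3) also give 48. Section 14.3 has six participants exposed to each Part 1 schedule. Section 11.1 gives the split as 36 participants on Ad4 and 12 on oral placebo.

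The allocation rule is in protocol section 10.1.1. It says "The first 6 participants successfully enrolled into the trial will be sequentially pre-allocated to treatment groups B, C, D, F, G and H", and that "the remaining participants will be block randomised into groups as follows". Block 1 has ten slots, with A and E twice and each other group once. The list then ends with "Blocks 2-6 (n=8/block): A, B, C, D, E, F, G, H".

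SAP section 5.1 has the same sentinels and the same Block 1, but its last line is "Blocks 2-5 (n=8/block): A, B, C, D, E, F, G, H".

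On strata, protocol section 14.1 says "Randomisation will be stratified on the basis of gender". Protocol section 10.2 and SAP section 6 say the same. The block list in both documents is printed as one numbered sequence with no mention of strata.

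On withdrawals, protocol section 12.8.1 commits to replacing participants who leave before the week 26 visit is complete, and expects 10–20% to withdraw. Neither document links any block to these replacements.

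**The concern.** Section 10.1.1 is the protocol's only statement of how many slots each Part 1 group receives. Its design shows that an exact total was intended: the second A and second E in Block 1 make up for the sentinels, who go only to the six Ad4 groups. A list built to finish level should finish at the planned size, and this one finishes one participant per group above it.

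Several things depend on that size. It sets the number of healthy volunteers given a replicating vector for which section 7.8 says there are no clinical data. The confidence intervals in protocol Table 7 are for n=6. The SAP table shells print 6 per group. SAP section 12.2.1.2 combines six participants from Part 1 with six from Part 2 to reach 12 per group; a group of seven would give 13.

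The two documents also give different block counts for the same step, so a reader checking the schedule cannot tell which one governed.

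**Working it through.** **Inputs.** Six sentinels, one each in B, C, D, F, G and H (protocol 10.1.1 and 14.1, SAP 5.1). Block 1 has ten slots: A and E twice, the others once (protocol 10.1.1, SAP 5.1). Later blocks have eight slots, one per group: five such blocks in protocol 10.1.1 and four in SAP 5.1. The target is 48, 6 per group, 36 on Ad4 and 12 on oral placebo (protocol 7.6 and 11.1).

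**Formulas.** Total = sentinels + Block 1 + 8 × (number of later blocks). Group size = sentinel slots + Block 1 slots + number of later blocks.

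**The planned figure, reproduced from the SAP list (four later blocks).**
- Total: 6 + 10 + 4 × 8 = 48.
- A and E: 0 + 2 + 4 = 6 each.
- B, C, D, F, G and H: 1 + 1 + 4 = 6 each.
- Ad4: 6 groups × 6 = 36. Oral placebo: 2 groups × 6 = 12.

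All four figures match the protocol's stated plan.

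**The protocol list (five later blocks).**
- Total: 6 + 10 + 5 × 8 = 56.
- A and E: 0 + 2 + 5 = 7 each.
- B, C, D, F, G and H: 1 + 1 + 5 = 7 each.
- Ad4: 6 × 7 = 42. Oral placebo: 2 × 7 = 14.
- Excess: 56 − 48 = 8, and 8/48 = 16.7%.

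**Could the sentinels lie outside the 48?** No. The protocol blocks alone give 10 + 40 = 50, with 7 in A and E and 6 elsewhere. That is neither 48 nor balanced.

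**Could block 6 be a reserve?** The size fits. Expected withdrawals are 10–20% of 48, or 4.8 to 9.6, and eight lies in that range. The mechanism is not described, however. A block holding one slot for each of A to H restores a group only if the replacement is matched to the slot of the group that lost a participant. If the replacement simply takes the next slot in a randomly ordered block, that slot belongs to the right group with probability 1/8.

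**Gender strata.** If the printed blocks were the list for each gender and both lists were filled, the totals with the sentinels would be 6 + 2 × 50 = 106 (protocol) or 6 + 2 × 42 = 90 (SAP). The printed list is therefore not a complete description of a stratified schedule. This does not show what schedule was actually used.

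**The case against.** The best defence is that a block list is not an enrolment target. The target of 48 is stated many times, and under the printed sequence the 48th allocation falls exactly at the end of block 5: 6 + 10 + 32 = 48. If enrolment stops there, block 6 is never opened and every group has six. This stands, and it limits the practical consequence.

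A second defence is that block 6 was meant for replacements. The protocol says that extra participants may be enrolled to replace early withdrawals, the block size fits the expected withdrawal rate, and one spare slot per group sits comfortably with section 12.8.1, which refers further replacement to the Trial Management Group when more than one participant in a group drops out for perceived safety or tolerability. This also stands as a possibility, so ending the list at block 5 is not the only acceptable correction. It does not remove the point: section 10.1.1 presents all the blocks as the allocation of the remaining participants, and nothing marks the last one as different.

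On strata, a reader might infer from the single printed sequence that randomisation was not stratified, and that groups of six could end up almost all of one gender. The documents do not support that. Three sections say that randomisation is stratified by gender, and SAP section 6 refers to a schedule produced by the trials unit's statisticians, which is not among the documents. A summary that leaves out the strata is incomplete; it does not establish an unstratified list.

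**Conclusion.** The count is exact and rests on no assumption: as written, protocol 10.1.1 allocates 56 participants, 7 per group (42 on Ad4, 14 on oral placebo), against a plan of 48, 6 per group (36 and 12). It also contradicts SAP 5.1, which reproduces the plan exactly. The error is eight slots, or 16.7%. A numbering slip in the protocol and an unlabelled reserve block would both explain it, and the documents do not settle which.

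A reader might go further and conclude that eight extra healthy volunteers will be dosed. That does not follow, because the repeated target of 48 can stop enrolment before block 6 is used.

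The gender point is a request for clarification only. Any probability of unbalanced or unequal groups would depend on an assumed gender mix and an assumed way of dividing the blocks between strata, and the documents give neither.

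**What to change.** Do one of two things in protocol section 10.1.1. Either end the list at block 5, as in SAP 5.1, or keep block 6 and label it as used only to replace withdrawals under section 12.8.1 and not counted towards the 48, with a sentence on how a replacement is matched to the group that lost a participant. Then make protocol 10.1.1 and SAP 5.1 identical.

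In the same edit, add a sentence to protocol 10.2 or 14.1 and to SAP 6 saying how the blocks are applied within gender strata, including where Block 1 sits.

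The cost is a few lines of text and a check against the schedule held by the trials unit. The SAP is dated 2021 and describes trial conduct in the past tense, so if Part 1 allocation is already complete, the equivalent step is a file note and a statement in the study report of the schedule used and the number allocated to each group. No analysis method changes.

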#### 10.1.4 GP NOTIFICATION

With the participant's consent, shortly after randomisation a letter should be sent to the general practitioner informing him/her of the trial and the participant's involvement in the trial.

## 10.2 RANDOMISATION CODES AND & UN-BLINDING

This is a single-blind, randomised trial with placebo controls. Participants will be block-randomised centrally to the study groups shown in Table 1, using a computer-generated algorithm with a back-up manual procedure. Randomisation will be stratified on the basis of gender. All participants in Part 1 and Part 2 will be blinded to the vaccine regime group to which they have been assigned. The laboratory teams undertaking immunological analysis will also be blinded to group and dosing regimen to prevent bias in analysis. The clinical team will remain unblinded to the vaccine regime of trial participants throughout.

## 10.3 CO-ENROLMENT GUIDELINES

Participants will be advised that they cannot enrol in any other trials during the period from screening to the final visit in Ad4HIV. All participants will be entered onto the TOPS (The Over volunteering Prevention System) database as a measure to prevent over volunteering.

If staff discover that a participant is enrolled on another study during this period, they must immediately contact the Principal Investigator for advice. Decisions will be reviewed on a case by case basis and participant safety will be the primary concern.

## 10.4 PARTICIPANT'S COMPLIANCE & ADHERENCE

In consenting to the trial, participants are consenting to trial treatment, trial follow-up and data collection. However, an individual participant may stop treatment early or be stopped early for any of the following reasons:

- Unacceptable adverse event
- Inadequate compliance with the protocol in the judgement of the treating physician
- Withdrawal of consent by the participant

As the volunteer's participation in the trial is voluntary, they may choose to discontinue the trial treatment at any time without loss of benefits to which they are otherwise entitled. Although the participant is not required to give a reason for discontinuing their trial treatment, a reasonable effort should be made to establish this reason while fully respecting his/her rights.

Participants should remain in the trial for the purpose of follow-up and data analysis (unless the volunteer withdraws their consent from all stages of the trial). Data will be kept and included for volunteer who stop follow-up early.

## 11 TREATMENT OF PARTICIPANTS

### 11.1 VACCINE PRODUCTS & ADMINISTRATION

#### **CN54gp140 / MPLA:**

CN54gp140 / MPLA will be provided by UK HIV Vaccine Consortium (UKHVC) in 2 mL Schott type 1 glass vials. One dose of CN54gp140/MPLA will be 100 $\mu$ g of protein and 5 $\mu$ g of MPLA, in a volume of 0.4mL.

#### **MVA-CN54:**

MVA-CN54 will be provided by UK HIV Vaccine Consortium in 2 mL Schott type 1 glass vials. One dose of MVA-CN54 delivers  $1.0 \times 10^8$ /TCID50 in a volume of 0.5 mL.

#### **Ad4-EnvCN54:**

Ad4-EnvCN54 will be provided by PaxVax as a lyophilised powder. One dose of Ad4-EnvCN54 delivers  $10^{10}$ VP per capsule.

#### **Oral Placebo**

Oral placebo capsules were developed by Patheon UK Ltd, to match the active Ad4-EnvCN54 oral capsule. Hypromellose (HPMC) capsule shells were filled with sucrose supplied as a white crystalline powder, and then coated with an enteric solution.

#### **Intramuscular Placebo**

Intramuscular placebo for injection vials were developed by Polymun Scientific Ltd; Austria, to match the active MVA-C investigational product. The placebo comprises a liquid formulation containing 20 mM Tris / 0.15 M NaCl (pH 7.5). Tris is used as buffer substance, sodium chloride for appropriate osmolality and hydrochloric acid for buffer pH adjustment.

Investigational medicinal product vials and bottles will be labelled and packaged according to regulatory requirements. The PI will ensure that staff administering the vaccines have been appropriately trained in the written procedures for delivery of the vaccines.

Investigators and trained members of the clinical team will be encouraged to administer the vaccine as soon as possible and within 2 hours of being removed from cold storage. The date and time of administration will be recorded in the Case Report Form (CRF) and medical notes.

Participants will receive I.M injections, and Ad4 or placebo administered orally, as described in the schedule of doses (Table 1). In Part I, 36 participants will receive Ad4CN54-Env in combination with CN54gp140, or MVA-CN54 and CN54gp140, whilst 12 participants will receive an oral placebo in combination MVA-CN54 and/or CN54gp140. Dosing will be at weeks 0 (Month 0), 12 (Month 3) and 24 (Month 6). The two best vaccine regimes from B-D (Ad4/gp140) and F-H (Ad4/MVA-C/gp140), provided they meet the pass criterion, will be expanded and 12 participants will be screened and enrolled for Part 2 of the study.

## 11.2 ACCOUNTABILITY FOR USED AND UNUSED SUPPLIES

The PI will ensure that the IMPs and placebos are stored and dispensed in accordance with the protocol and local pharmacy procedures, and that records are maintained of receipt, dispensing and return/destruction of all supplies. The PI must ensure that all IMP and placebo supplies are kept in a secure area accessible only to authorised individuals, and maintained in storage at the following temperatures:

- Ad4-EnvCN54 at  $-20 \pm 5$  °C
- Matched oral placebo at  $-20 \pm 5$  °C
- MVA-CN54 at  $\leq -70$  °C
- CN54gp140/MPLA at 2–8 °C
- Matched I.M placebo at 2–8 °C

Upon receipt of supplies, a designated member of staff will conduct an inventory and acknowledge receipt to the supplier. A record must be kept of all Ad4-EnvCN54, MVA-CN54 and CN54gp140 / MPLA used during the trial. This will include the description (lot numbers and expiry dates) and quantity of IMP received at the trial site and date of receipt, as well as a record of when (date of administration) and to whom (volunteer trial ID) it was dispensed.

At the end of the trial, IMP accountability will be checked by the designated member of staff responsible for the inventory and trial monitors. The Sponsor and the PI will retain copies of the complete IMP accountability records. All unused supplies will be retained at the trial site until the Sponsor gives instructions for their return/destruction.

### 11.3 VACCINATION SCHEDULE – PART 1 & PART 2

The doses, methods and schedule of immunisation are described below.

**Table 1: Schedule of Doses and Method of Vaccinations**

PART I						PART II		
	Group	N	Month 0	Month 3	Month 6		N	Vaccinations 1,2,&3
ARM 1	A	6	Oral placebo	CN54gp140 + Oral placebo +I.M placebo	CN54gp140 + Oral placebo +I.M placebo		12	Selected dosage from Part I
	B	6	Ad4-EnvCN54	CN54gp140 + Oral placebo +I.M placebo	CN54gp140 + Oral placebo +I.M placebo			
	C	6	Ad4-EnvCN54	CN54gp140 + Ad4-EnvCN54 +I.M placebo	CN54gp140 + Oral placebo +I.M placebo			
	D	6	Ad4-EnvCN54	CN54gp140 + Ad4-EnvCN54 +I.M placebo	CN54gp140 + Ad4-EnvCN54 +I.M placebo			
ARM 2	E	6	Oral placebo	CN54gp140 + MVA-CN54 + Oral placebo	CN54gp140 + MVA-CN54 + Oral placebo			
	F	6	Ad4-EnvCN54	CN54gp140 + MVA-CN54 + Oral placebo	CN54gp140 + MVA-CN54 + Oral placebo			
	G	6	Ad4-EnvCN54	CN54gp140 + MVA-CN54 + Ad4-EnvCN54	CN54gp140 + MVA-CN54 + Oral placebo			
	H	6	Ad4-EnvCN54	CN54gp140 + MVA-CN54 + Ad4-EnvCN54	CN54gp140 + MVA-CN54 + Ad4-EnvCN54			
		48					max 12	

